17.2.4 Immunogenicity Subgroup Analysis of Adverse Events

A listing of immunogenicity data and TEAEs will be provided containing subject ID, age, gender, study treatment start and stop date, all dates with positive ADA result, all dates with positive nAb results, preferred term of TEAE, TEAE start and stop date, CTCAE toxicity grade, and flags for SAE, irAE, IRR, and/or reason for permanent treatment discontinuation, as well as ADA status group.

Only subjects who are pre-existing positive, transient treatment-emergent positive, or persistent treatment-emergent positive will be listed.

17.3 Clinical Laboratory Evaluation

17.3.1 Hematology and Chemistry Parameters

Laboratory results will be classified according to the NCI-CTCAE criteria version 4.03. Non-numerical qualifiers (with the exception of fasting flags) will not be taken into consideration in the derivation of CTCAE criteria (e.g., hypokalemia Grade 1 and Grade 2 are only distinguished by a non-numerical qualifier and therefore Grade 2 will not be derived). Additional laboratory results that are not part of NCI-CTCAE will be presented according to the categories: below normal limit, within normal limits and above normal limit (according to the laboratory normal ranges).

Quantitative data will be summarized using simple descriptive statistics (mean, SD, median, Q1, Q3, minimum, and maximum) of actual values and changes from baseline for each nominal visit over time (unscheduled measurements would therefore not be included in these summaries as described in [Section 11](#)). End of Treatment visit will be summarized separately. The changes computed will be the differences from baseline. Qualitative data based on reference ranges will be described according to the categories (i.e. Low, Normal, High).

Abnormalities classified according to NCI-CTCAE toxicity grading version 4.03 will be described using the worst grade. For those parameters which are graded with two toxicities such as potassium (hypokalemia/hyperkalemia), the toxicities will be summarized separately. Low direction toxicity (e.g. hypokalemia) grades at baseline and post baseline will be set to 0 when the variables are derived for summarizing high direction toxicity (e.g. hyperkalemia), and vice versa.

For **WBC differential counts** (total neutrophil [including bands], lymphocyte, monocyte, eosinophil, and basophil counts), the absolute value will be used when reported. When only

percentages are available (this is mainly important for neutrophils and lymphocytes, because the CTCAE grading is based on the absolute counts), the absolute value is derived as follows:

Derived differential absolute count = (WBC count) * (Differential %value / 100)

If the range for the differential absolute count is not available (only range for value in % is available) then Grade 1 will be attributed to as follows:

- Lymphocyte count decreased:
 - o derived absolute count does not meet Grade 2-4 criteria, and
 - o % value < % LLN value, and
 - o derived absolute count \geq 800/mm³
- Neutrophil count decreased:
 - o derived absolute count does not meet Grade 2-4 criteria, and
 - o % value < % LLN value, and
 - o derived absolute count \geq 1500/mm³

For **calcium**, CTCAE grading is based on Corrected Calcium. Corrected Calcium is calculated from Albumin and Calcium as follows

Corrected Calcium (mmol/L) = Calcium (mmol/L) + 0.02 [40 - Albumin (g/L)].

Liver function tests: Alanine aminotransferase (ALT), aspartate aminotransferase (AST), and total bilirubin are used to assess possible drug induced liver toxicity. The ratios of test result over upper limit of normal (ULN) will be calculated and classified for these three parameters during the on-treatment period.

Summary of liver function tests will include the following categories. The number and percentage of subjects with each of the following during the on-treatment period will be summarized:

- ALT \geq 3 \times ULN, ALT \geq 5 \times ULN, ALT \geq 10 \times ULN, ALT \geq 20 \times ULN
- AST \geq 3 \times ULN, AST \geq 5 \times ULN, AST \geq 10 \times ULN, AST \geq 20 \times ULN
- (ALT or AST) \geq 3 \times ULN, (ALT or AST) \geq 5 \times ULN, (ALT or AST) \geq 10 \times ULN, (ALT or AST) \geq 20 \times ULN
- TBILI \geq 2 \times ULN
- Concurrent ALT \geq 3 \times ULN and TBILI \geq 2 \times ULN
- Concurrent AST \geq 3 \times ULN and TBILI \geq 2 \times ULN
- Concurrent (ALT or AST) \geq 3 \times ULN and TBILI \geq 2 \times ULN
- Concurrent (ALT or AST) \geq 3 \times ULN and TBILI \geq 2 \times ULN and ALP > 2 \times ULN
- Concurrent (ALT or AST) \geq 3 \times ULN and TBILI \geq 2 \times ULN and ALP \leq 2 \times ULN or missing

Concurrent measurements are those occurring on the same date.

Categories will be cumulative, i.e., a subject with an elevation of AST $\geq 10 \times \text{ULN}$ will also appear in the categories $\geq 5 \times \text{ULN}$ and $\geq 3 \times \text{ULN}$. Liver function elevation and possible Hy's Law cases will be summarized using frequency and percentage.

An evaluation of Drug-Induced Serious Hepatotoxicity (eDISH) plot will also be created to graphically display

- peak serum ALT(/ULN) vs. peak total bilirubin (/ULN) including reference lines at ALT $> 3 \times \text{ULN}$ and total bilirubin $> 2 \times \text{ULN}$.
- peak serum AST(/ULN) vs. peak total bilirubin (/ULN).

In addition, a listing of all TBILI, ALT, AST and ALP values for subjects with a post-baseline TBILI $\geq 2 \times \text{ULN}$, ALT $\geq 3 \times \text{ULN}$ or AST $\geq 3 \times \text{ULN}$ will be provided.

Parameters with NCI-CTC grades available:

The laboratory toxicities will be tabulated using descriptive statistics (count and percentage) during the on-treatment period. The denominator to calculate percentages for each laboratory parameter is the number of subjects evaluable for CTCAE grading (i.e., those subjects for whom a Grade 0, 1, 2, 3, or 4 can be derived).

- The summary of laboratory parameters by CTCAE grade table will include number and percentage of subjects with Grade 1, 2, 3, 4, 3/4, and any grade (1 to 4) laboratory abnormalities during the on-treatment period.
- The shift table will summarize baseline CTCAE grade versus the worst on-treatment CTCAE grade. The highest CTCAE grade during the on-treatment period is considered as the worst grade for the summary.

The above analyses apply to hematology and chemistry evaluations which can be graded per CTCAE, i.e.:

- Hematology:
Hemoglobin (HB), Leukocytes (white blood cell decreased), Lymphocytes (lymphocyte count increased/decreased), Neutrophils / Absolute Neutrophils Count (ANC) (neutrophil count decreased), Platelet Count (PLT) (platelet count decreased).
- Serum chemistry:
Albumin (hypoalbuminemia), Alkaline Phosphatase (alkaline phosphatase increased), Alanine Aminotransferase (ALT) (ALT increased), Amylase (serum amylase increased), Aspartate Aminotransferase (AST) (AST increased), Total Bilirubin (blood bilitubin increased, Cholesterol (cholesterol high), Creatinine (creatinine increased), Creatine Kinase (CPK increased), Potassium (hypokalemia/hyperkalemia), Sodium (hyponatremia/hypernatremia), Magnesium (hypomagnesemia/hpermagnesemia), Calcium (hypocalcemia/hypercalcemia), Glucose (hypoglycemia/hyperglycemia), Gamma Glutamyl Transferase (GGT) (GGT increased), Lipase (lipase increased), Phosphates (hypophosphatemia), Triglycerides (hypertriglyceridemia).

Parameters with NCI-CTC grades not available:

Hematology and chemistry evaluations which can't be graded per CTCAE criteria will be summarized as:

- Number of subjects with shifts from baseline normal to at least one result above normal during on-treatment period
- Number of subjects with shifts from baseline normal to at least one result below normal during on-treatment period

In this study, these apply to the following parameters:

- Hematology:
Hematocrit, Red Blood Cell (RBC), Reticulocytes, Mean Corpuscular Hemoglobin (MCH), Mean Corpuscular Volume (MCV), Mean Corpuscular Hemoglobin Concentration (MCHC).
- Serum Chemistry:
Chloride, C-Reactive Protein, Lactate Dehydrogenase (LDH), Total Protein, Total Urea, Uric Acid.

Subjects without post baseline laboratory samples will be excluded from analyses with respect to values after the baseline.

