7.1.2.1 Part A

During the treatment period, the following assessments will be performed (see [Appendix I](#) for the detailed schedule):

- The EQ-5D and FACT-M will be completed by subjects prior to any study related procedures at Week 7, and then once every 6 weeks thereafter while on treatment.
- Subject interviews (optional) by a trained experienced interviewer to collect subjects' current experience with their disease and its treatment (at Week 13 and at 6 months of treatment, see [Section 7.7.1](#)).
- AEs and concomitant medications will be documented at each trial visit.
- ECOG PS will be assessed at Day 1 (unless the Screening ECOG PS was performed within 3 days prior to Day 1) and at each study visit thereafter.
- Physical examinations will be performed at each treatment visit until Week 13 and every 6 weeks thereafter. Such examinations will include a comprehensive skin examination for tumor.
- Vital signs and body weight will be assessed in each treatment visit.
- A 12-lead ECG (assessed prior to infusion and 2 hours \pm 20 minutes after the end of infusion) will be assessed at each treatment visit up to and including Week 13, and every 6 weeks thereafter until 18 months, after which subjects no longer require on treatment ECGs.
- The laboratory hematology, hemostaseology will be assessed at each visit. Core serum chemistry tests will be assessed at Weeks 1, 7, 9, and 11 and after Week 13, every 2 weeks thereafter and full serum chemistry (including core chemistry) will be assessed at Weeks 3, 5, and 13 and then every 6 weeks thereafter. In addition, for subjects with liver metastases at Baseline, samples for ALT, AST, total bilirubin, and alkaline phosphatase determination will be collected at Weeks 2, 4, and 6. A basic urinalysis (dipstick) will be performed at each on treatment visit. If the basic urinalysis is abnormal, a full urinalysis should be performed.
- A urine β -HCG pregnancy test will be performed at each treatment visit (before each administration of the study drug) for females of childbearing potential.
- Tumor evaluation (see [Section 7.3](#)) will be performed at Week 7, and then once every 6 weeks thereafter, with a tumor assessment visiting time window of 5 days prior to dosing. After Week 55 (12 months) from the first treatment, tumor assessments will be every 12 weeks.

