7.1.2.2 Part B

During the treatment period, the following assessments will be performed (see [Appendix I](#) for the detailed schedule):

- The EQ-5D and FACT-M will be completed by subjects prior to any study related procedures at Week 7, and then once every 6 weeks thereafter while on treatment.
- Subject interviews (optional) by a trained experienced interviewer to collect subjects' current experience with their disease and its treatment (at Week 13 and at 6 months of treatment, see Section 7.7.1).
- AEs and concomitant medications will be documented at each treatment visit.
- ECOG PS will be assessed at Day 1 (unless the Screening ECOG PS was performed within 3 days prior to Day 1) and at each treatment visit thereafter.
- Physical examinations (directed to signs and symptoms) will be performed at each visit through Week 13 and then every 6 weeks thereafter. Such examinations may include a comprehensive skin examination for tumor.
- Vital signs and body weight will be assessed in each treatment visit (body weight may be collected within 3 days prior to infusion).
- The laboratory hematology, hemostaseology will be assessed at each treatment visit. Core serum chemistry tests will be assessed at each visit. A basic urinalysis (dipstick) will be performed on the Day 1 visit prior to administration of study drug. If the basic urinalysis is abnormal, then a full urinalysis should be performed. Urinalysis after Day 1 should be performed as clinically indicated.
- A urine or serum β -HCG pregnancy test according to local practice will be performed at Weeks 1, 5, 9, and 13 and then every 4 weeks thereafter for females of childbearing potential. Results of the most recent pregnancy test should be available prior to the next treatment.
- Tumor evaluation (see Section 7.3) will be performed at Week 7, and then once every 6 weeks thereafter, with a tumor assessment visiting time window of 5 days prior to dosing. After Week 55 (12 months) from the first treatment, tumor assessments will be every 12 weeks.
- PK samples will be collected from all subjects receiving avelumab within 2 hours prior to each study drug infusion through Week 7, every 6 weeks through Week 25, and then at 12-week

intervals thereafter while on treatment. Post study drug administration samples will be collected at the end of infusion at Weeks 1, 7, and 25.

- Free T4, and TSH will be measured at Week 1, Week 7, Week 13, and every 6 weeks during the treatment period.

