Hormone	ACTH, ANA, ANCA, RF, TSH, and T4 For Part A, to be assessed at the Screening visit, Week 13, Week 25, and at the End-of Treatment visit. For Part B, only ACTH, ANA, ANCA, RF, T4, and TSH will be collected at Screening visit, Week 13, Week 25, End-of-Treatment, and Safety Follow-up visits. T4 and TSH to be assessed in Week 1, Week 7, Week 13, and then every 6 weeks while on treatment and at the 30-day End-of-Treatment visit.
FSH (if applicable)	

ADA = antidrug antibody, ACTH=adrenocorticotrophic hormone, ALT=alanine aminotransferase, ANA=antinuclear antibody, ANC=absolute neutrophil count, ANCA=antineutrophil cytoplasmic antibody, aPTT=activated partial thromboplastin time, AST=aspartate aminotransferase, BUN=blood urea nitrogen, CRP=C-reactive protein, FSH=follicle-stimulating hormone, GGT=gamma-glutamyltransferase, INR=international normalized ratio, LDH=lactate dehydrogenase, MCH=mean corpuscular hemoglobin, MCHC=mean corpuscular hemoglobin concentration, RBC=red blood cell, RF=rheumatoid factor; TSH=thyroid-stimulating hormone, T4=free thyroxine, WBC=white blood cell.

* Core serum chemistries in Part A and Part B

** Included in core serum chemistries only for Part B

If a subject has a clinically significant abnormal laboratory test value that is not present at baseline, the test will be repeated weekly and the subject will be followed until the test value has returned to the normal range or the Investigator has determined that the abnormality is chronic or stable.

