		W1	W3	W5	W7	W9	W11	W13					
Written informed consent	X												
Inclusion / exclusion criteria	X												
Medical history	X												
Demographic data	X												
EQ-5D and FACT-M ^e	X				X			X	6 weekly		X		
Subject interviews ^f	X							X ^f	6 months ^f				
HBV, HCV, and HIV testing	X												
Physical examination, including height at Screening ^g	X	X	X	X	X	X	X	X	6 weekly	X	X	X	
Vital signs	X	X	X	X	X	X	X	X	2 weekly	X	X	X	
Weight	X	X	X	X	X	X	X	X	2 weekly	X	X	X	
ECOG PS ^h	X ^h	X	X	X	X	X	X	X	2 weekly	X	X	X	
Enrollment (if eligible) ⁱ	X												
ECG ^j	X									X	X	X	
Hematology and hemostaseology	X	X	X	X	X	X	X	X	2 weekly	X	X	X	
Core serum chemistry ^k		X	X	X	X	X	X	X	2 weekly			X	
Full serum chemistry ^l	X									X	X		
Urinalysis ^m	X	X								X	X	X	
β-HCG pregnancy test ⁿ	X	X		X		X		X	4 weekly		X	X	

Part B

Measure	Screening/ Baseline Assessments	Treatment Phase ^a								Follow-up ^b			
	Day -18 to First Treatment	V1	V2	V3	V4	V5	V6	V7	Until Progression	Discontinuation Visit Within 7 days of decision to discontinue ^b	End-of-Treatment Visit 30 (±5) Days after Last Treatment ^{c,d}	Safety Follow-up Visit 90 Days (±1 week) after Last Treatment	Long-term Follow-up Every 3 months ^b
		W1	W3	W5	W7	W9	W11	W13					
Tumor evaluation / staging (CT Scan / MRI / mapping skin lesions / tumor markers / other established methods) ^{b,o,p}	X				X			X	6 weekly up to 12 months then 12 weekly		X		X ^b
Documentation of AEs and concomitant medication	X	X	X	X	X	X	X	X	2 weekly	X	X	X	
ACTH, ANA, ANCA, and RF	X							X	Week 25 and as indicated		X	X	
Free T4 and TSH	X	X			X			X	6 weekly		X	X	
PK sampling ^q		X ^q	X ^q	X ^q	X ^q			X ^q	6 weekly to Week 25 ^q then every 12 weeks	X	X	X	
ADA sampling ^r		X	X	X	X			X	6 weekly to Week 25 then every 12 weeks		X	X	
Pretreatment and study drug administration ^s		X	X	X	X	X	X	X	2 weekly				
CCI													
Tumor tissue (biopsy) ^u	X												
CCI													

Part B

Measure	Screening/ Baseline Assessments	Treatment Phase ^a								Follow-up ^b			
	Day -18 to First Treatment	V1	V2	V3	V4	V5	V6	V7	Until Progression	Discontinuation Visit Within 7 days of decision to discontinue ^b	End-of-Treatment Visit 30 (±5) Days after Last Treatment ^{c,d}	Safety Follow-up Visit 90 Days (±1 week) after Last Treatment	Long-term Follow-up Every 3 months ^b
		W1	W3	W5	W7	W9	W11	W13					
		D1	D15	D29	D43	D57	D71	D85					
CCI													
CCI													
CCI													

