- If there are two or more unscheduled assessments with non-missing results and the same distance to the planned study day, the assessment prior to the planned study day will be used in deriving visit window. For example, if the lab assessment was done on both study day -1 and 1, then the assessment on -1 study day will be used for visit windowing.

Table 2 Visit Window Definition for Safety Assessment

| Assigned Study Day (Inclusive) | | Planned Study Day (AWTARGET) | Analysis Visit (N) (AVISITN) | Analysis Visit (AVISIT) | Assessment |
|--------------------------------|-----------|------------------------------|------------------------------|-------------------------|----------------------|
| From (AWLO) | To (AWHI) | | | | |
| ~ | 1 | 1 | 1 | Baseline | Lab, Vital Sign |
| 5 | 11 | 8 | 2 | Week 2 Day 5-11 | |
| 12 | 18 | 15 | 3 | Week 3 Day 12-18 | Lab, Vital Sign |
| 19 | 25 | 22 | 4 | Week 4 Day 19-25 | Core Serum Chemistry |
| 26 | 32 | 29 | 5 | Week 5 Day 26-32 | Lab, Vital Sign |
| 33 | 39 | 36 | 6 | Week 6 Day 33-39 | Core Serum Chemistry |
| 40 | 50 | 43 | 7 | Week 7 Day 40-50 | Lab, Vital Sign |
| 51 | 64 | 57 | 9 | Week 9 Day 51-64 | Lab, Vital Sign |
| 65 | 78 | 71 | 11 | Week 11 Day 65-78 | Lab, Vital Sign |
| 79 | 92 | 85 | 13 | Week 13 Day 79-92 | Lab, Vital Sign |
| 93 | 106 | 99 | 15 | Week 15 Day 93-106 | Lab, Vital Sign |
| 107 | 120 | 113 | 17 | Week 17 Day 107-120 | Lab, Vital Sign |
| 121 | 134 | 127 | 19 | Week 19 Day 121-134 | Lab, Vital Sign |
| 135 | 148 | 141 | 21 | Week 21 Day 135-148 | Lab, Vital Sign |
| 149 | 162 | 155 | 23 | Week 23 Day 149-162 | Lab, Vital Sign |
| 163 | 176 | 169 | 25 | Week 25 Day 163-176 | Lab, Vital Sign |
| 177 | 190 | 183 | 27 | Week 27 Day 177-190 | Lab, Vital Sign |
| 191 | 204 | 197 | 29 | Week 29 Day 191-204 | Lab, Vital Sign |
| 205 | 218 | 211 | 31 | Week 31 Day 205-218 | Lab, Vital Sign |

Further windows can be calculated based on the following general algorithm starting from the planned study day in Week X:

$$\text{Planned study day in Week X} = (X - 1) * 7 + 1$$

$$\text{Assigned study days (inclusive)} = (X - 6) \text{ days to } (X + 7) \text{ days}$$

Missing data and imputation rules:

Unless otherwise specified in this SAP, all data will be evaluated as reported and no imputation of missing values will be done.

In all subject data listings imputed values will be presented. In all listings imputed information will be flagged.

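### In Part B, calcium is graded on albumin-corrected values but no dosing visit schedules albumin, so the worst on-treatment calcium grade misses every scheduled dosing-visit result

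*SAP*

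**What the plan says.** **Grading rule.** In section 17.3.1 of both SAPs, "CTCAE grading is based on Corrected Calcium. Corrected Calcium is calculated from Albumin and Calcium as follows". The Part B formula adds 0.02 mmol/L to calcium for each g/L by which albumin is below 40. Neither SAP says what to do when albumin is absent.

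**Panels.** Protocol section 7.4.3, Table 7, marks some full-chemistry tests with one asterisk, meaning "Core serum chemistries in Part A and Part B". Calcium has it and albumin does not. A double asterisk, "Included in core serum chemistries only for Part B", marks only amylase and lipase.

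**Part B timing.** Protocol section 7.1.2.2: "Core serum chemistry tests will be assessed at each visit". In the Part B schedule in Appendix I, the row "Full serum chemistry" is marked only at Screening, Discontinuation and End of Treatment. Safety Follow-up is core only.

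**Part A timing.** Protocol section 7.1.2.1: "full serum chemistry (including core chemistry) will be assessed at Weeks 3, 5, and 13 and then every 6 weeks thereafter".

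**Analysis rules, Part B SAP.** Section 11 states that, unless otherwise specified, "all data will be evaluated as reported and no imputation of missing values will be done". It ends the on-treatment period 30 days after last dose, or the day before a new anti-cancer drug if that is earlier. Section 17.3.1 takes the highest grade in that period for the shift table, and limits each percentage to subjects for whom a grade can be derived.

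**The concern.** The grade needs two inputs, and at Part B dosing visits only one of them is collected. With no imputation and no fallback, a calcium result without albumin is neither Grade 0 nor abnormal; it is ungraded.

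Two distortions follow. First, the worst on-treatment calcium grade would describe the time around stopping treatment and not the treatment period. Core tests such as potassium are graded at every visit in the same table, and nothing tells the reader that the calcium row is different. Second, the calcium percentages would rest mainly on subjects who stopped avelumab, a selected group. Safety is a secondary objective of Part B, and protocol section 5.1 gives Part B a confirmatory role for some approvals.

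**Working it through.** The plan states no figure that depends on this rule, so there is nothing to reproduce. The check sets the sampling schedule against the grading rule.

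**1. Scheduled samples at dosing visits.** Visits are every 2 weeks from Week 1. For a last dose in Week W, the number of post-baseline dosing visits is (W − 1)/2.

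| Last dose | Part B calcium results | Part B albumin results | Part A full panels, same span |
|---|---|---|---|
| Week 7 | 3 | 0 | 2 |
| Week 13 | 6 | 0 | 3 |
| Week 25 | 12 | 0 | 5 |
| Week 55 | 27 | 0 | 10 |

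**2. Discontinuation visit, Part B.** Every subject who stops has one, within 7 days of the decision, with full chemistry (protocol section 7.1.3 and Appendix I). Assume that the decision comes by the next planned dose, day 14 after the last. The visit is then by day 14 + 7 = 21, inside the 30-day limit. A decision after day 23 can put it outside, since 23 + 7 = 30.

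**3. End-of-Treatment visit, Part B.** It is planned for day 30 ± 5, that is days 25 to 35, which is 11 possible days. Days 25 to 30, or 6 of the 11, are inside the on-treatment period if no new anti-cancer drug has started.

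**4. Gradable scheduled time points per subject, Part B.** Usually 1 or 2 for a subject who has stopped, and 0 for a subject still on treatment at cut-off.

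**5. Part A.** Biweekly visits from Week 1 to Week 51 number 26. Full chemistry falls at Weeks 3, 5, 13, 19, 25, 31, 37, 43 and 49, which is 9. Visits without albumin: 26 − 9 = 17, or 17/26 = 65%. Week 1 is normally a pre-dose baseline visit; without it the share is 16/25 = 64%. This is a share of samples. Per subject, the panels at Weeks 3 and 5 make nearly everyone evaluable.

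**6. Size of the correction.** Shift = 0.02 × (40 − albumin in g/L). Albumin of 35, 30 and 25 g/L gives 0.10, 0.20 and 0.30 mmol/L. These are illustrative values; the documents report no albumin data.

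**The case against.** The strongest reply is that the gap is narrower than it looks.

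- **Calcium can be graded on treatment.** A reader might infer from the schedule that no on-treatment calcium in Part B is gradable. The documents do not support that: the on-treatment period runs to 30 days after last dose, which usually takes in the Discontinuation visit and sometimes End of Treatment. Both visits have full chemistry. Unscheduled panels also count, and protocol section 7.4.3 has new clinically significant abnormal values repeated weekly, though that does not guarantee albumin. This stands.
- **Same-day albumin is not required in so many words.** The only same-date definition in section 17.3.1 is in the liver-test block, so a programmer might pair calcium with an older albumin. This stands in part. The no-imputation rule speaks against it, and in Part B the older value would often be from Screening. If pairing were allowed, the grades would rest on an unwritten choice.
- **Calcium data are not lost.** Values and changes are summarized by visit, results are categorized Low/Normal/High, and all results are listed with flags. Protocol section 7.4.1.1 exempts from adverse event reporting only laboratory findings below Grade 3 that are without symptoms, do not lead to discontinuation and are not otherwise medically important. This stands, so what is lost is mainly low-grade, laboratory-derived grades.
- **It is one descriptive parameter.** No efficacy analysis or type I error is touched. This stands and sets the severity.

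**Conclusion.** The point holds as a minor one. Followed as written, the Part B rules leave every scheduled dosing-visit calcium result out of the graded and shift tables, and drop from the denominator any subject still on treatment at cut-off who has no unscheduled full panel. This assumes that calcium and albumin must come from the same visit, as the no-imputation rule implies. The documents do not say how many subjects will be on treatment at cut-off, so the loss in the denominator cannot be sized.

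It would go too far to infer that calcium events become invisible, since the ungraded summaries, the listings and the adverse event tables remain. It would also be wrong to read the 65% for Part A as subjects lost.

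The sampling gap also affects the other tests that Part B lists for grading but collects only in the full panel: albumin, GGT, creatine kinase, cholesterol and triglycerides. They need no second input, but their worst on-treatment grade has the same limited coverage.

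**What to change.** In section 17.3.1 of both SAPs:

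1. Grade corrected calcium where albumin from the same visit exists, or albumin within a short stated window, flagged as such. Otherwise grade uncorrected calcium. An open-ended carry-forward should be avoided, because in Part B it would often reach back to Screening.
2. Alongside, tabulate grades on uncorrected calcium for all on-treatment values, with every subject who has an on-treatment calcium value in that denominator.
3. Footnote the Part B tables to say that albumin, GGT, creatine kinase, cholesterol and triglycerides are scheduled on treatment only at Discontinuation and End of Treatment.

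The cost is a few sentences, one derivation and one extra table, with no new samples. The downside is that uncorrected grades may misclassify subjects with low albumin, by 0.2 mmol/L at an albumin of 30 g/L. The two tables should therefore be read together.
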